5.3. Exclusion Criteria

- 1. Current enrollment in another investigational protocol
- 2. Screening or enrollment 6MWD of < 50 meters
- 3. Difference > 15% between first and second enrollment 6MWD
- 4. Acute or chronic impairment other than dyspnea (eg, angina pectoris, intermittent claudication) limiting the ability to comply with walk test or other study requirements
- 5. Forced expiratory volume 1/FVC ratio < 0.65 after administration of bronchodilator
- 6. Extent of emphysema greater than the extent of fibrotic change (honeycombing, reticular changes) on HRCT scan
- 7. Acute myocardial infarction within the past 6 months
- 8. Nitrate use
- 9. Hypersensitivity to sildenafil or any component of the formulation
- 10. Presence of aortic stenosis (AS)
- 11. Life-threatening arrhythmia within 1 month of evaluation
- 12. Poorly controlled diabetes mellitus requiring insulin therapy
- 13. Second-degree or third-degree atrioventricular (AV) block on electrocardiogram
- 14. Severe chronic heart failure: defined by left ventricular ejection fraction (EF) < 25%
- 15. Presence of idiopathic hypertrophic subaortic stenosis (IHSS)
- Hypotension (systolic blood pressure [SBP] < 100 mm Hg or diastolic blood pressure [DBP] < 50 mm Hg); (symptomatic orthostatic hypotension)
- 17. Uncontrolled systemic hypertension (SBP > 180 mm Hg or DBP > 100 mm Hg)
- Known penile deformities or conditions (eg, sickle cell anemia, multiple myeloma, leukemia) that may predispose to priapism
- 19. Aspartate aminotransferase (AST)/serum glutamic pyruvic transaminase (SGPT) or alanine aminotransferase (ALT)/serum glutamic oxaloacetic transaminase (SGOT) > 3 times the upper limit of normal ranges
- 20. Renal impairment: creatinine clearance < 30 mL/minute
- 21. Current drug or alcohol dependence
- 22. Retinitis pigmentosa
- 23. History of vision loss
- 24. History of nonarteritic ischemic optic neuropathy

- 25. Recently initiated pulmonary rehabilitation within 30 days of enrollment. Subjects will be prohibited from starting pulmonary rehabilitation during the trial. Subjects who are currently undergoing maintenance pulmonary rehabilitation at study entry will be asked to maintain their levels of rehabilitation for the duration of the trial.
- 26. Any investigational therapy as part of a clinical trial for any indication, within 30 days of enrollment
- Start or change in dose of treatment for IPF investigational agent (interferon γ-1b, pirfenidone, etanercept, N-acetylcysteine, and any other investigational agent intended to treat IPF), corticosteroids, or cytotoxic agents, within 30 days of enrollment
- 28. Due to drug-drug interactions, the following agents will be prohibited: bosentan. Subjects taking strong CYP3A4 inhibitors (eg, azole antifungals, clarithromycin, diclofenac, doxycycline, erythromycin, imatinib, isoniazid, nefazodone, nicardipine, propofol, protease inhibitors, quinidine, telithromycin, troleandomycin, verapamil—not an inclusive list) will be asked to stop taking the CYP3A4 inhibitor at least 30 days prior to enrollment. However, if the subject requires the CYP3A4 inhibitor (PI judgment), as long as the dose is not changed throughout the study, the subject will be allowed to concurrently take the CYP3A4 inhibitor.
- 29. Treatment for PH with prostaglandins (eg, epoprostenol, treprostinil), endothelin-1 antagonists (eg, bosentan, sitaxsentan, ambrisentan), or any other phosphodiesterase inhibitor (eg, tadalafil, vardenafil) within 30 days of enrollment
- 30. The addition or discontinuation of calcium channel blockers, digitalis, diuretics, or vasodilators within 30 days of enrollment. Dosage must be stable for 7 days prior to enrollment (except for diuretics).
- 31. Listed for lung transplantation
- 32. Supplementation with L-arginine
- 33. Concurrent use of grapefruit juice or St. John's wort
- 34. Pregnant or lactating women
- Resting SpO₂ (oxygen saturation measured using pulse oximetry) < 92% with 6 liters of supplemental oxygen

As stated in exclusion criteria 26–30, subjects included in this study will be allowed to use prespecified concomitant medications, including investigational and conventional drugs with

the only requisite that the dose does not change, as outlined in exclusion criteria 27 and 30. Permitted agents are not expected to influence subjects' hemodynamic parameters, their 6MWT performance, or study drug blood levels. Randomization is expected to balance the groups with respect to these concurrent agents. Furthermore, inclusion of a treatmentexperienced population will increase the generalizability of the study.

Study drug will be used with caution in subjects taking alpha-blockers; may cause hypotension. Safety of this combination may be affected by other anti-hypertensives and intravascular volume depletion. Subjects should be hemodynamically stable prior to initiating therapy. Precautions will be taken in subjects with penile implants (e.g. consultation with urology specialist) before initiation of study drug.

With the current lung allocation system, the mean waiting time for lung transplantation, once the person is listed, is approximately 3 months. In order to limit study dropouts, subjects listed for lung transplantation will be excluded from this study.

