All subjects will return at week 6. In addition to the items described under the week 1 visit (with the exception of the evaluation of orthostatic hypotension), subjects will undergo a 6MWT with Borg scale measurement, PFT (spirometry and DLco), BNP measurement, QOL and dyspnea questionnaires, and functional classification. If consent has been given, blood will be drawn for research purposes. The study diary will be reviewed, and an additional 6 weeks of sildenafil will be dispensed. Compliance to the study medication will be assessed using pill counts. Week 6 visit will be recorded if it occurs within 7 days of the subject's

scheduled visit time (eg, the week 6 visit can occur anytime between 5 and 7 weeks after starting study drug).

5.4.2.5. Week 12

All subjects will return at week 12 for the final first-period study visit. The assessments for this visit will be the same as for week 6, with the addition of ABG measurement. Also the evaluation of orthostatic hypotension will occur prior to the administration of study drug and 1 hour after administration of study drug. If consent has been given, blood will be drawn for research purposes. During this visit, all subjects will be transitioned to the open-label phase of the protocol and receive a 6-week supply of sildenafil at 20 mg 3 times daily. Compliance to the study medication will be assessed using pill counts. Week 12 visit will be recorded if it occurs within 7 days of the subject's scheduled visit time (eg, the, week 12 visit can occur anytime between 11 and 13 weeks after starting study drug). One additional blood pressure measurement will be obtained 1 hour after administration of study drug.

5.4.2.6. Week 13

All subjects will return at week 13 for a targeted medical history, physical examination, and laboratory values (CBC and serum chemistries) to monitor for side effects and for research purposes. Also the evaluation of orthostatic hypotension will occur. The study diary will be reviewed, and compliance to sildenafil will be assessed using pill counts. Week 13 visit will be recorded if it occurs within +/- 2 days of the student's scheduled visit time

5.4.2.7. Week 18

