As outlined in section 3.4, sildenafil appears to be generally well-tolerated in subjects with advanced lung disease. In a study of 14 subjects with IPF treated with sildenafil (see section 4.1), 2 subjects had sildenafil stopped due to side effects attributed to the medication (diarrhea and transient hypotension). In that study, 1 subject experienced chest pain during the follow up test, 1 subject complained of mild intermittent diarrhea and headaches, another complained of mild intermittent headaches, and a fourth complained of blurry vision. The remaining 8 subjects experienced no AEs. In a large trial of sildenafil for primary PH (160

subjects), most AEs were mild-to-moderate for all treatment groups. Over 12 weeks, only 2 SAEs, postural hypotension and left ventricular dysfunction, were considered to be related to sildenafil (Galie et al. 2005).

Monitoring for side effects will include questioning on every study visit and encouragement to call the investigator about headache, diarrhea, visual changes, chest pain, palpitations, worsening dyspnea, peripheral edema, diaphoresis, and dizziness. As outlined in section 5.3, subjects with unstable cardiovascular disease or pre-existing ophthalmologic conditions will be excluded from the study. On every study visit, investigators will obtain a medical history and perform a complete physical examination. One additional blood pressure measurement will be obtained 1 hour after administration of study drug on the day of enrollment and on week 12 visit.

Orthostatic hypotension has occurred rarely in subjects receiving sildenafil (<2%), with a similar rate reported by those receiving placebo (Zusman RM et al. Am J Cardiol 1999; 83:35C). To monitor for this unlikely but potential complication, an orthostatic hypotension evaluation will be performed at screening, enrollment (pre and post study drug administration), wk 1, wk 12 (pre and post sildenafil administration), and wk 13 visits.

Beginning with the enrollment evaluation, subjects with symptomatic orthostatic hypotension will be discontinued from study drug but may remain in the trial. Symptoms of orthostatic hypotension are those that develop on assuming the erect posture and usually resolve on resuming the recumbent position. They may include lightheadedness, dizziness, blurred vision, weakness, fatigue, cognitive impairment, nausea, palpitations, tremulousness, headache, and neck ache.

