5.6.3 Study Drug Discontinuation

Study drug will be stopped in any subject with SBP < 100 mm Hg or DBP < 50 mm Hg. Subjects with chest pain, palpitations, worsening peripheral edema, S3 gallop, or diaphoresis will have a 12-lead ECG and a 2D-echocardiogram performed as soon as possible. Study

drug will be stopped in subjects with acute coronary syndromes, AV block, life-threatening arrhythmias, left ventricular dysfunction (EF < 25%), or clinically significant visual changes.

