5.9 Concomitant Medications

The following medications will not be allowed during the course of the study: alpha-blockers (eg, doxazosin), bosentan, CYP3A4 inhibitors (eg, azole antifungals, clarithromycin, diclofenac, doxycycline, erythromycin, imatinib, isoniazid, nefazodone, nicardipine, propofol, protease inhibitors, quinidine, telithromycin, troleandomycin, and verapamil—not an inclusive list), prostaglandins (eg, epoprostenol and treprostinil), endothelin-1 antagonists (eg, bosentan, sitaxsentan, and ambrisentan), and any other phosphodiesterase inhibitor (eg, tadalafil and vardenafil).

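### Section 5.9 bars alpha-blockers and CYP3A4 inhibitors outright, but section 5.3 lets a subject who needs a CYP3A4 inhibitor stay on it and has no criterion excluding alpha-blocker users.

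*Protocol*

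**What the plan says.** **Alpha-blockers.** Section 5.9 of the protocol opens its list of barred drugs with them: "The following medications will not be allowed during the course of the study: alpha-blockers (eg, doxazosin". It gives no exception and does not separate new from continuing use. The text that closes section 5.3, after criterion 35, says "Study drug will be used with caution in subjects taking alpha-blockers; may cause hypotension" and continues "Safety of this combination may be affected by other anti-hypertensives and intravascular volume depletion". It then asks for hemodynamic stability before therapy starts. No exclusion criterion names alpha-blockers.

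**CYP3A4 inhibitors.** The 5.9 list continues with "bosentan, CYP3A4 inhibitors (eg, azole antifungals, clarithromycin" and further agents, again without exception. Criterion 28 in 5.3 asks subjects on strong CYP3A4 inhibitors to stop at least 30 days before enrollment. It then adds that if the investigator judges the drug necessary, "as long as the dose is not changed throughout the study, the subject will be allowed to concurrently take the CYP3A4 inhibitor".

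**Safeguards.** Criterion 16 excludes low blood pressure. Blood pressure is taken 1 hour after dosing at enrollment and week 12 (5.4.2.2, 5.4.2.5). Section 5.6.2 says "subjects with symptomatic orthostatic hypotension will be discontinued from study drug but may remain in the trial", and section 5.6.3 says "Study drug will be stopped in any subject with SBP < 100 mm Hg or DBP < 50 mm Hg".

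**The concern.** Eligibility is decided from section 5.3, and conduct during the study is judged against section 5.9. Where the two differ, two sites can handle the same candidate differently, and a subject enrolled correctly under one section can be a deviation under the other. Section 9.5 plans reports on the number of ineligible participants enrolled, and for these drugs that count depends on which section is applied.

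There is also a safety side. The protocol itself says that study drug with an alpha-blocker may lower blood pressure, and it gives drug interaction as the reason for criterion 28. The exposure is not confined to one arm, because at week 12 "all subjects will be transitioned to the open-label phase of the protocol and receive a 6-week supply of sildenafil".

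**Working it through.** No statistical calculation applies. The check sets the rules side by side and counts what can be counted.

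| Drug class | Section 5.3 | Section 5.9 | Can both be obeyed? |
|---|---|---|---|
| Alpha-blockers | Named in 0 of 35 criteria; closing text describes cautious use | Barred, no exception | Yes, by applying 5.9; not by a site using 5.3 alone |
| CYP3A4 inhibitors | Strong inhibitors: stop 30 days before, or continue at a constant dose if required | Barred, no exception, no qualifier of strength | Not for a subject kept on one under criterion 28 |

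**CYP3A4 overlap.** Criterion 28 names 15 agents or classes, from azole antifungals to verapamil. Section 5.9 names the same 15. Every example that criterion 28 may allow is therefore barred by 5.9. The scopes also differ: criterion 28 is limited to strong inhibitors, and 5.9 is not.

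**Possible reconciliations for alpha-blockers.**
1. *Section 5.9 bars only new starts.* Its wording covers the whole course of the study and makes no such distinction.
2. *The vasodilators in criterion 30 include alpha-blockers.* That criterion bars only starting or stopping within 30 days of enrollment. It would leave stable use open, so the mismatch with 5.9 would remain.

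**Longest possible exposure for one affected subject.** Sildenafil arm: weeks 0 to 24 = 24 weeks. Placebo arm: weeks 12 to 24 = 12 weeks, open label. Dose: 3 × 20 mg = 60 mg/day. This is the trial's ordinary schedule. It bounds the exposure and says nothing about how often the problem would arise.

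**Monitoring (Table 4).** Orthostatic evaluation takes place at screening, enrollment and weeks 1, 12 and 13, which is 5 of 8 in-person visits (week 28 is a telephone call). It is not scheduled at weeks 6, 18 and 24. Those visits do include history, physical examination, adverse-event review and concomitant-medication review. The two reviews take place at every visit from enrollment to week 24, and section 5.6.2 adds side-effect questioning at every study visit.

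**Effect on the analysis.** Randomization is stratified by clinical center (10.7), and analyses use all randomized participants by intention to treat (10.6). Differences between sites in whom they enroll therefore do not favor an arm in the primary comparison.

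**The case against.** The strongest reply concerns alpha-blockers. A caution is not a permission, and the stricter section satisfies both texts. The protocol often pairs caution with a bar. Section 5.6.2 advises caution with bosentan, retinitis pigmentosa and recent myocardial infarction, although bosentan is prohibited and the other two are exclusions. Section 5.3 also says that permitted agents are not expected to affect hemodynamic parameters, and a drug said to risk hypotension does not fit that description.

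Much of this stands. A reader might infer that 5.3 makes alpha-blocker users eligible, and the documents do not go that far. What remains is that the caution sentence sits in the eligibility section and states how study drug will be used in this trial. It stands next to another working instruction, on specialist consultation for penile implants, and no criterion beside it excludes these subjects. The wording in 5.6.2 reads as general product precautions and can stay.

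The reply does not reach the CYP3A4 conflict. There an express permission meets an express prohibition.

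**Conclusion.** The inconsistency is real and should be corrected. It is direct for CYP3A4 inhibitors and softer for alpha-blockers, where the risk comes from a site relying on 5.3 alone. It affects safety and consistent eligibility and deviation decisions across sites.

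Two stronger readings are not supported. One is that weeks 6, 18 and 24 offer nothing beyond history and physical examination. Table 4 schedules adverse-event and medication review at each of them, and the medication review is the check most likely to find a barred drug. The other is that the trial's result is at risk. Nothing here changes power, introduces bias or alters the primary analysis.

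The protocol does not give the share of candidates on either drug class, so no count of affected subjects is offered. The conclusion rests on the wording alone.

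**What to change.** **Alpha-blockers.** Keep the ban in 5.9. Add alpha-blocker use to the exclusion criteria in 5.3 with a 30-day washout, and delete the caution sentence and the follow-on sentence about the combination. The 30 days match criterion 28 and fit the 6-week window between screening and enrollment (30 < 42 days). Allowing stable alpha-blocker use instead is not advised, because it would contradict the statement in 5.3 that permitted agents are not expected to affect hemodynamics.

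**CYP3A4 inhibitors.** Either carry the criterion 28 exception into 5.9 and limit both sections to strong inhibitors, or delete the exception. If it is kept, qualify the same statement in 5.3, which also says that permitted agents are not expected to affect study drug blood levels. The sponsor chooses between the two on clinical grounds.

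**Cost.** Wording in 5.3 and 5.9 at the next amendment. Candidates on alpha-blockers would be excluded or need washout, and deleting the CYP3A4 exception would also exclude those who cannot stop such a drug. Section 5.6.2 needs no change.

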5.4 Study Design and Study Visits

[figure not shown]

Figure 5.3: Outline of Study Design

5.4.1. Study Design Summary

Enrolled subjects will undergo a baseline 6MWT and have clinical data and blood collected. Subjects will then be given sildenafil 20 mg or placebo orally 3 times per day for 12 weeks. Study visits will occur at 1, 6, and 12 weeks, with additional data collected. A 6MWT and additional clinical data and blood will be performed/collected after 12 weeks. The primary endpoint for this study will be change in 6MWD over 12 weeks. The endpoint will be dichotomized into $(1) \ge 20\%$ improvement in 6MWD and (2) < 20% improvement in 6MWD. Subjects unable to complete the 6MWT at 12 weeks will be considered to have a < 20% improvement in 6MWD. A major secondary endpoint will be change in QOL over 12 weeks. All subjects will take part in a second 12-week open-label phase of the protocol once they have completed the first period. This second study period will assign all subjects to

sildenafil 20 mg 3 times daily and evaluate the short-term effects of treatment and longerterm (24-week) safety profile (see Figure 5.3).

5.4.2. Study Visits

Subjects who meet entry criteria will review the informed consent, a written description of the purpose, procedures, and risks of the study, with the principal investigator (PI), coinvestigator, or study coordinator, and all questions will be answered. The informed consent form will be signed by the subject at screening. No protocol-specific procedures will be performed until the subject has signed and dated an informed consent form. This includes the screening procedures.

5.4.2.1. Screening

A history and physical examination (including pulse oxygen saturation), PFTs, arterial blood gases (ABGs), HRCT, and histopathologic review (if applicable) will be performed. Subjects will then complete a questionnaire to collect contact information, demographics, medical history, current therapies, and current symptoms. An echocardiogram will be performed to evaluate cardiac function and look for AS and IHSS. A complete blood count, serum chemistry profile, urinalysis, and an electrocardiogram (ECG) and a hCG (serum) pregnancy test (in women of childbearing potential) will be obtained.

All PFTs will be conducted by study personnel not directly involved in the treatment of the subjects. For screening purposes DLco adjusted for hemoglobin will be used. The hemoglobin value will be obtained from the ABGs. If a second spriometry and DLco are required per protocol (>14 days from screening) at enrollment visits this repeat DLco will be used to determine study eligibility.

A 6MWT will be performed as described in the STEP-IPF Manual of Operating Procedures (MOOP). If the distance of this walk is less than 50m, the subject is not eligible for enrollment into the study.

At the screening visit, subjects will be tested for resting SpO₂ levels while breathing room air. Subjects with SpO₂ \ge 88% will be walked on room air. Those below 88% will receive

resting supplemental oxygen, titrated until their resting SpO_2 levels reach 92%, and then will perform the 6MWT on that oxygen flow. Subjects will walk until they complete the 6 minutes or until their O_2 levels drop below 80% for 6 seconds. Upon dropping below 80%, the walk test will be halted and the distance walked to that point will be recorded.

During subsequent visits, subjects will have their resting SpO_2 levels measured at room air. Subjects will, if applicable, also have their resting SpO_2 levels measured on the same oxygen flow as assigned at the screening visit. Subjects whose resting SpO_2 levels do not reach 88% while receiving the assigned oxygen flow will not be walked and will have a zero recorded for their 6MWD. Subjects at or above 88% will walk (after receiving the oxygen flow assigned at the screening visit) until they complete 6 minutes or until their O_2 levels drop below 80% for 6 seconds. The distance walked will be recorded.

Subjects with symptomatic orthostatic hypotension at the screening visit will be excluded from the study. Subjects with asymptomatic orthostatic hypotension at screening may still be enrolled in the trial.

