5.4.2.2. Enrollment

Eligible subjects will return for enrollment. The enrollment visit will occur no more than 6 weeks after the screening evaluation is completed. If oxygen was newly prescribed during the screening oxygen titration 6MWT, at least 7 days must separate the onset of oxygen use and the enrollment visit. Subjects will undergo a targeted history and physical examination.

Subjects will undergo two 6MWTs on the oxygen flow assigned at screening. If the distance between these two walks is greater than 15%, the subject is not eligible for enrollment. If the distance of either of the two walks is less than 50m, the subject is not eligible for enrollment. At each walk, the Borg dyspnea scale (BDS) will be measured.

PFT and ABG measurement will be performed, and blood will be drawn for a BNP level measurement. If consent has been given, blood will be drawn for research purposes. The gender sub study, QOL and dyspnea questionnaires will be completed, and NYHA functional classification obtained. Female subjects of child-bearing potential will be instructed to use 2

forms of nonhormonal contraception throughout the study duration. Also the evaluation of orthostatic hypotension will occur prior to administration of study drug and 1 hour after administration of study drug.

During the enrollment visit, subjects will receive training in the proper administration and storage of study drug and diary use and will receive a 6-week supply of study drug. Subjects will be instructed to start study drug at the enrollment visit. Subsequent study visits (1, 6, and 12 weeks) will be scheduled from the start date of study drug. One additional blood pressure measurement will be obtained 1 hour after administration of study drug on the day of enrollment.

If the enrollment visit occurs within 14 days of the screening visit, some procedures may not need to be performed at this visit, and the results of the screening measurements may be used as the enrollment measurements.

5.4.2.3. Week 1

All subjects will return at week 1 for a targeted medical history, physical examination, and laboratory values (CBC and serum chemistries) to monitor for side effects. Also the evaluation of orthostatic hypotension will occur. The study diary will be reviewed and subject compliance will be assessed by pill counts. Week 1 visit will be recorded if it occurs within +/- 2 days of the subject's scheduled visit time.

5.4.2.4. Week 6

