5.4.2.10. Long Term Follow up

Following the above visits, subjects will have no further study visits. However, study staff will conduct a long-term follow up 5 years after the subject completes the study visits. There are no plans to contact the subject directly during this follow up. Study staff will be asked to collect survival information from the social security death index or other forms of public information.

Table 4. Table of Study Visits

	Screen	Enroll	Wk 1	Wk 6	Wk 12	Wk 13	Wk 18	Wk 24	Wk 28
Informed consent	Х								
Medical history	Х	Х	Х	Х	Х	Х	Х	Х	
Physical exam	Х	Х	Х	Х	Х	Х	Х	Х	
Additional blood pressure		Х			Х				
Pulmonary function testing	X ¹	X ^{,2,3}		X ³	X ³		X ³	X ³	
HRCT	X ⁵								
Review surgical lung biopsy	Х								
(if applicable)									
ABG	Х	X^2			Х			Х	
Pregnancy test	Х								
ECG	Х								
6MWT and Borg scale	Х	X ⁶		Х	Х		Х	Х	
Complete blood cell count	Х	X^2	Х	Х	Х	Х	Х	Х	
and serum chemistries									
Urinalysis	Х								
Research blood draw and		Х		Х	Х		Х	Х	
urinalysis (if consent granted)									
ECHO	Х								
BNP		Х		Х	Х		Х	Х	
Evaulation for orthostatic	Х	X^7	Х		X ⁸	Х			
hypotension									
QOL assessment (SF-36,		Х		Х	Х		Х	Х	
EuroQol, St. George's									
Respiratory Questionnaire,									
and ICECAP)									
Gender substudy		Х							
questionnaire									
NYHA functional		Х		Х	Х		Х	Х	
classification									
UCSD SOBQ		Х		Х	X X		Х	Х	
Evaluate for acute		Х	Х	Х	Х	Х	Х	Х	
exacerbation									
Review adverse events		Х	Х	Х	Х	Х	Х	Х	Х
Review concomitant meds		Х	Х	Х	Х	Х	Х	Х	
Dispense subject diary ⁴		Х	Х	Х	Х	Х	Х		
Review subject diary and pill			Х	Х	Х	Х	Х	Х	
count									
Dispense study treatment		Х		Х	Х		Х		

¹ Full PFTs (spirometry with pre and post bronchodilator, lung volumes, and DLco)

² If the enrollment visit occurs within 14 days of the screening visit, the procedure may not need to be performed at this visit, and the results of the screening measurements may be used as enrollment measurements.

³ Spirometry and DLco

⁴ Subject may be dispensed another diary if there is no more room to record information in the one he or she has.

⁵Not necessary if acceptable HRCT (please see STEP IPF MOOP for criteria) available within 3 months of screening

⁶ Two walks prior to enrollment with at least 1 hour between walks

⁷ Evaluate pre and post study drug administration – blinded phase

⁸ Evaluate pre and post study drug administration – open label phase

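### The only pregnancy test is at screening and contraception is first instructed at enrollment, so up to 6 weeks before first dose are covered by neither

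*Protocol*

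**What the plan says.** Criterion 34 in section 5.3 excludes "Pregnant or lactating women". Section 5.4.2.1 (Screening) supports it with one test: "a hCG (serum) pregnancy test (in women of childbearing potential) will be obtained". In Table 4 the pregnancy-test row has a single mark, under Screen. The procedures listed for the enrollment visit in section 5.4.2.2 do not include a pregnancy test.

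On timing, section 5.4.2.2 states: "The enrollment visit will occur no more than 6 weeks after the screening evaluation is completed". On treatment start it states: "Subjects will be instructed to start study drug at the enrollment visit". Contraception first appears in the same section: "Female subjects of child-bearing potential will be instructed to use 2" nonhormonal methods for the duration of the study.

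For some other measurements the protocol limits how long a screening value may be used. Footnote 2 to Table 4, attached to the enrollment entries for pulmonary function, arterial blood gas and blood count with chemistries, reads: "If the enrollment visit occurs within 14 days of the screening visit, the procedure may not need to be performed at this visit". Where spirometry and DLco have to be repeated because more than 14 days have passed, section 5.4.2.1 adds that "this repeat DLco will be used to determine study eligibility".

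**The concern.** An exclusion for pregnancy protects a subject only if her status is known when she takes the first dose. Here the test that establishes it may be six weeks old by then, and the text asks for no contraception in between. A woman could therefore pass screening correctly, conceive before enrollment or have been too early in pregnancy for the screening test, and start study drug although criterion 34 is meant to keep her out. The enrollment visit includes a targeted history and physical examination, but these do not reliably detect an early pregnancy.

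What is at stake is the safety of a small number of women. The efficacy comparison is not affected. From enrollment onward contraception is instructed for the rest of the study, so the point is confined to the interval before first dose.

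**Working it through.** No power or alpha figure is involved. The check sets the schedule side by side and adds simple arithmetic.

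**Sequence of events**

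| Step | When | Source |
|---|---|---|
| Serum hCG, the only test | Screening | Section 5.4.2.1; Table 4 |
| Enrollment visit | Up to 6 weeks after screening is completed | Section 5.4.2.2 |
| First contraception instruction | Enrollment visit | Section 5.4.2.2 |
| First dose | Enrollment visit | Section 5.4.2.2 |

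**Length of the uncovered interval**

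- The protocol's own limit is 6 weeks: 6 × 7 = 42 days from completed screening to enrollment. The interval is therefore 0 to 42 days.
- The clock starts when screening is completed, not when blood is drawn for hCG. If screening takes d days after the draw, the test can be 42 + d days old at first dose.

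**Comparison with the 14-day limit**

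- At the maximum interval, with screening done in one day: 42 − 14 = 28 days lie beyond the point at which DLco, blood gases and blood count with chemistries have to be renewed. The excess is larger if screening is spread over several days.
- If enrollment falls within 14 days of screening, none of the interval lies beyond that limit.

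**Women concerned**

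- Younger women can enter. Age above 50 years is one of four minor diagnostic criteria (section 5.2.2), and section 5.2 requires three of the four.
- The protocol does not give the share of subjects who are women of childbearing potential. Assuming 0.5% to 3% of the planned 170:
  - 0.005 × 170 = 0.85
  - 0.03 × 170 = 5.1
- That is about 1 to 5 women. It counts women to whom the gap applies, not expected pregnancies, which would be fewer. With 1:1 allocation, about half of them (0.4 to 2.6) would receive sildenafil in the first 12 weeks.

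**The case against.** The strongest reply is that nothing in the protocol is contradictory. Pregnant women are excluded, women of childbearing potential are tested by serum hCG, and two methods of contraception are instructed when treatment starts. A second test would be an added safeguard. Section 10.7 also has the randomization call made only once all eligibility criteria are met, so a woman known or suspected to be pregnant on that day could not be enrolled. This is right, and it limits the point to unrecognized pregnancy. It does not close the gap, because section 10.7 adds no test.

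The comparison with DLco is also imperfect. The repeated measurements serve partly as baselines for change from enrollment, and the ECG and echocardiogram, which also bear on eligibility, are done only at screening. The 14-day rule is therefore not a general standard that the pregnancy test breaches. It does show that the protocol already renews one eligibility measurement when the screening value has aged, and pregnancy status can likewise change within weeks.

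Section 5.8 refers to the Manual of Operating Procedures for details of the pregnancy test, and consent is signed at screening. Neither the manual nor the consent form is available here, and either could add a test or earlier advice. The claim is accordingly about the protocol text. Table 4 fixes when the test is done, and nothing in the protocol says that another document adds to it.

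Finally, the sections on contraindications and warnings do not mention pregnancy, so the protocol does not itself document a fetal risk. The concern rests on the protocol's own decision to exclude pregnant women.

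**Conclusion.** The point holds. The protocol schedules one pregnancy test, at screening, and places both the first contraception instruction and the first dose at a visit that may be 42 days after screening is completed. With the schedule followed exactly, an unrecognized early pregnancy can reach first dose in breach of criterion 34.

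The consequence is small: about 1 to 5 women of childbearing potential under an assumed 0.5% to 3% of 170, fewer actual pregnancies, and no effect on the efficacy result. The conclusion assumes that neither the operating manual nor the consent form already covers the interval. It is a low-priority improvement, worth making because it costs little.

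**What to change.** Add an Enroll mark to the pregnancy-test row of Table 4, so that women of childbearing potential have hCG repeated at enrollment and the result is known before first dose. As a minimum, require the repeat when more than 14 days have passed since screening, in line with footnote 2. No extra blood draw is needed, since at this visit "blood will be drawn for a BNP level measurement" in every subject.

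Give the two-method contraception instruction at screening, when the hCG test is done, and repeat it at enrollment.

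The cost is one mark in the table, one added sentence in section 5.4.2.1, and one more hCG assay in a few women, whose first dose waits for the result. The change is more than administrative, so under section 12.4 it needs IRB approval at each of the 12 sites. It is best bundled with the next amendment.
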